## **3.2.**Rationale for the Brainsway H1-Coil Deep Brain rTMS

Transcranial magnetic stimulation (TMS) is a non-invasive technique used for treating smoking cessation by stimulating the brain, as described above. However, the standard figure-8 coils have been shown to have a major effect mostly confined to the superficial cortical regions under the windings of the coil. The intensity of the electric field decreases rapidly deeper in the brain (Eaton, 1992; Maccabee et al, 1990; Tofts, 1990; Tofts et al, 1991). Therefore, in order to stimulate deep brain regions, a very high intensity is needed. Such intensity cannot be reached by the magnetic stimulators available today, using standard circular or figure-8 coils. Moreover, the intensity needed to effectively stimulate deeper brain regions would over-stimulate cortical regions leading to undesirable side effects.

The innovative DTMS system was thus developed by Brainsway Ltd. and intended for deep brain stimulation as an aid to smoking cessation. Mathematical models in conjunction with tests performed in a phantom model and clinical studies demonstrated the ability of the system to stimulate, by means of the HADD-Coil, deep brain regions. We hypothesize that the activation of deep brain regions and their interconnecting fibers may serve as a new approach in the treatment of neuropsychiatric illnesses with a prominent advantage over the standard coil which is unable to affect regions as deep as the HADD-Coil.

## 3.3.Intended Use

The Brainsway DTMS device is intended as an aid to smoking cessation.

## 3.4.Principles of Use

The HADD-Coil device technology is based on applying deep brain TMS by means of repetitive pulse trains at a determined frequency. A pre-selected treatment protocol is assumed to activate deep brain regions and their interconnecting fibers. This, in turn, may affect the mechanisms involved in the pathophysiology of mental illnesses on one hand, as well as the rewarding circuits, motivation and pleasure on the other hand.

The treatment protocol will start with localization of the optimal spot on the scalp for stimulation of the right abductor pollicis brevis muscle and determination of the individual motor threshold. The coil will then be placed 6 cm anterior to the motor spot.

Each daily treatment session will consist 60 rTMS trains of 10 Hz for 3 seconds with inter-train interval (ITI) of 15 seconds (a total of 1800 stimuli per session) over the prefrontal and insular cortices. Subjects in the control group will receive sham treatment in a similar manner. In the inactive sham treatment, some of the HADD-Coil windings are disconnected and no electric current flows through them. Additionally, the HADD-Coil windings are connected in series to a secondary coil, which is located at the connection between the cooling air pipe and the helmet, far from the patient head. The role of the secondary coil is to increase the auditory output and increase the overall coil inductance. Increasing the inductance leads to a decrease in the output electric field of the coil in the sham mode.

## 3.5.Study Procedure

The detailed procedures are described in the Instructions for Use in the Investigator's Brochure filed in the study center file. Following is a brief summary. The transition between active and sham modes is performed using a magnetic card reader controller. Prior to treatment, the operator must determine the position for the optimal APB motor cortex stimulation (in which the minimal stimulation intensity is required to induce visible motor activation). The operator inserts his operator card into the card reader to activate the real mode. After finding the position on the subject's head which requires the minimal stimulator output for reaching the motor threshold for

activation of the APB, the operator measures the location on the p subject's cap, using the cap's flexible ruler, as explained in the Instructions for Use in the Investigator's Brochure. The operator then moves the coil to the treatment location and attaches it to the subject's head, as explained in the Instruction for Use. The operator inserts the subject's treatment card programmed to activate either real or sham treatment mode according to the treatment group to which the patient has been randomized. The study personnel do not have any knowledge of whether the treatment mode or sham mode is being activated by the subject's treatment card. Thus, all study personnel, including the operator, the independent rater and study subjects will be blinded to the treatment being administrated. In addition, all the subjects will be TMS-naïve, with no prior experience with TMS. Subjects will be told that face and hand twitching may occur due to either sham or active treatment and they will be instructed to sit with their arms crossed and folded. The independent rater will only see the subject on the morning of the next treatment day. This procedure will guarantee double blinding and reduce any potential bias in the clinical study.

## 4. OVERALL RATIONALE FOR THE STUDY

In light of the positive results of the safety and efficacy, feasibility trial in Beer Yakov Mental Health Center with the DTMS treatment with the HADD-coil for treatment of smoking cessation (as described in section 2.3), a controlled, randomized, double-blind trial will be carried out, in which the DTMS treatment will be compared to sham treatment. This study is meant to confirm a lack of bias in the results of the pilot study. The Brainsway DTMS device is intended as an aid to smoking cessation. A study design was chosen that would evaluate the safety and effectiveness for this intended use. Treatment will be administered over a 6 week period and follow-up assessments will be conducted at 4 months. The treatment period is sufficient to investigate the effects of the DTMS treatment.

The clinical study design includes multiple measurements of safety and effectiveness parameters. The design is meant to demonstrate that the device shows superiority compared to sham treatment over six treatment weeks, at the 4 months follow up. The study design allows the results to clearly demonstrate that DTMS treatment is superior to sham treatment for the intended treatment paradigm.

The aim of the study is to evaluate the safety and efficacy of DTMS compared to sham treatment as an aid to smoking cessation in chronic ( $\geq 10$  cigarettes/day) cigarette smokers.

## 5.1. Primary Objective

The primary objective is to compare the four-week continuous quit rate (CQR), representing abstinence during a consecutive 4 week period, between the two treatment groups. Weekly abstinence is defined as a subject's self-report (in diary) of no smoking (0 cigarettes/day during the whole week), confirmed by urine cotinine levels  $\leq 200$  ng/ml. A missing confirmatory test will be considered negative, if the previous and the following weekly or 4 month follow-up confirmatory tests are negative. Quit rates are defined as the ratio of the number of patients meeting the quit criterion for at least 4 consecutive weeks to the number of patients initially treated and having at least one post-baseline assessment.

#### 5.2. Secondary Objectives

- To compare the four-week continuous quit rate (CQR), representing abstinence during a consecutive 4 week period, between the two treatment groups. Weekly abstinence is defined as a subject's self-report (in diary) of no smoking (0 cigarettes/day during the whole week), confirmed by urine cotinine levels <200ng/ml. A missing confirmatory test will be considered negative, if the previous and the following weekly or 4 month follow-up confirmatory tests are negative. Quit rates are defined as the ratio of the number of patients meeting the quit criterion for at least 4 consecutive weeks to the total number of patients having assessments during a consecutive 4 week period.
- The secondary objective is to compare number of cigarettes smoked per day (per diary data) for all subjects.

#### **5.3.Exploratory Objectives**

Additional endpoints include:

- Weekly point prevalence abstinence rates, defined as the ratio of the number of subjects meeting the weekly abstinence criterion to the number of subjects initially treated and having at least one post-baseline assessment.
- Number of cigarettes smoked per day (per diary data) for non-quitter subjects only.
- Effect on withdrawal symptoms as measured by weekly scales measuring nicotine craving and dependence/withdrawal, including Fagerstrom Test for Nicotine Dependence (FTND), Minnesota Nicotine Withdrawal Scale Self-Report (MNWS), Tobacco Craving Questionnaire–Short Form (TCQ-SF) and Nicotine Craving Scale.

## **5.4.Safety Objectives**

- To evaluate the incidence, severity and frequency of all Adverse Events (AE), related and unrelated to the device treatment, including seizures.
- To evaluate possible cognitive changes using the Mini Mental State Exam (MMSE) and the Buschke Selective Reminding Test (BSRT) cognitive tests.
- Vital signs and hearing loss measured by auditory threshold testing will be evaluated.

## 6. OVERVIEW OF STUDY DESIGN

The proposed study will compare smoking cessation in two groups of subjects. One group will be assigned to the DTMS treatment (HADD-coil), and the other group will be assigned to the sham treatment (sham coil). This is a prospective, 6 month, double blind, randomized, controlled, multi-center trial in outpatients recruited in both academic and private research centers. A maximum of 270 subjects will be enrolled in the study. The study population will consist of chronic ( $\geq$ 10 cigarettes/day) cigarette smokers motivated to stop smoking and who represent the target population for the use of the DTMS treatment. Subjects of all ethnic and gender categories, ages ranging between 22-70 years will be included in the study. The study is comprised of three periods:

- 1. Pre-study screening and Baseline Phase;
- 2. Treatment Phase; and
- 3. Follow up Phase.

Subjects will be screened for study eligibility according to the inclusion and exclusion criteria described in the study protocol. Subjects who meet the eligibility criteria and are willing to sign an informed consent form will be enrolled in the study. The subjects' demographic and baseline characteristics, as well as their overall medical condition will be assessed prior to treatment administration.

Eligible patients will be randomized to one of two treatment groups. Randomization will be employed to avoid bias in the assignment of subjects to treatment groups, to increase the likelihood that known and unknown subject attributes (e.g. demographic and baseline characteristics) are evenly balanced across treatment groups, and to enhance the validity of statistical comparisons across the treatment groups.

In the *treatment trial period* patients will be randomized to one of two treatment groups (treatment or sham). The treatment group will receive 3 weeks of daily DTMS treatments with the HADD-coil, followed by 3 weekly DTMS treatments, for a total of 18 treatment sessions and 1800 magnetic stimulations per treatment session. The control group will receive the same treatments with a sham coil, for a total of 18 treatment sessions, as well. Each DTMS session will consist of 60 trains. The duration of each train will be three seconds and the inter-train interval will be 15 seconds. All subjects will undergo the same treatment regimen, regardless of the assigned treatment group.

Subjects will be asked to select a target quit date (TQD within 7-14 days of the first treatment session. Participants will be asked to refrain from smoking nicotine for at least two hours prior to the baseline visit and prior to each treatment session. Prior to treatment stimulation onset, a smoking related cue will be presented to the subject. Immediately after the offset of the smoking cue presentation (while memory is reactivated) active or sham DTMS stimulation will be administered. It has recently been demonstrated that in nicotine-deprived smokers, reward and attention circuits are reactivated by mere exposure to smoking-related images, in contrast with neutral images (Due et al., 2002). The preliminary study conducted with the Brainsway DTMS device (described in section 2.3) found that induction of craving by a smoking cue immediately prior to DTMS over the prefrontal and insular cortices induces a stronger effect on nicotine addiction relative to DTMS treatment alone. We propose that presentation of the smoking cue causes the nicotine-related memories and associated craving to become activated and therefore, labile for interference, as previously suggested (Amiaz et al., 2009; Dudai, 2006).

The study design is directed towards a comparison, between active treatment and sham, at 6 weeks and 4 months follow-up.

Efficacy will be assessed using the primary efficacy measure of abstinence, where abstinence is defined as a subject's self-report (in diary) of no smoking (0 cigarettes/day), confirmed by urine cotinine levels  $\leq 200$  ng/ml. Additionally, several subject assessment scales will be used during the course of the study to assess nicotine craving and nicotine withdrawal symptom.

Safety will be assessed, including monitoring of adverse events, vital signs, physical examination and auditory threshold testing. The Mini-Mental State Exam (MMSE) and the Buschke Selective Reminding Test (BSRT) cognitive tests will also be used to assess changes in cognition and memory during the study period.

Details on the timing of all treatments and assessments are given in the Time and Events Schedule in Attachment 1 of the Protocol. The anticipated enrollment period is approximately six months and therefore, the complete duration of the study is expected to last 1 year, during which time 270 subjects will be enrolled at approximately 20 sites. The masked, randomization status will be maintained for the entire time of subject enrollment, until the last subjects have completed the study.

## 7. STUDY POPULATION

# 7.1.General Considerations

The study will recruit male and female chronic cigarette smokers from the general population, aged 22-70 who are motivated to quit smoking. Subjects will be recruited by advertisements in the newspapers and specific websites and treated in academic and private research centers. Informed consent will be obtained from potential subjects according to local and national IRB requirements. Candidates will be screened with a medical interview, physical examination and a safety screening questionnaire for transcranial magnetic stimulation (Keel 2001).

# 7.2. Subject Inclusion Criteria:

Subjects must fulfill the following criteria:

- Male or female subjects, 22-70 years old.
- Current, chronic (≥10 cigarettes/day) smokers, who smoke for more than 1 year, with no period of abstinence for greater than 3 months during the past year.
- Subjects who are motivated to quit smoking (with responses "very likely," or "somewhat likely" to the motivation questionnaire).
- Satisfactory answers on safety screening questionnaire for transcranial magnetic stimulation (Keel 2001).
- Gave informed consent for participation in the study.

# 7.3. Subject Exclusion Criteria:

- Currently on Nicotine Replacement Therapy (NRT) or smoking cessation drugs (e.g., Zyban, Chantix, etc.) or undergoing behavioral smoking cessation interventions.
- Cognitive or functional disability, diagnosed according to DSM-5 criteria.
- Active psychiatric disorder according to DSM-5 (Axis I and Axis II) criteria within the last year.
- Current alcohol or other substance abuse or dependence.
- Alcohol or other substance abuse or dependence during the last 12 months before recruitment.
- Subject is smoking any other form of tobacco or other substances.
- Subject is taking psychotropic medications on a regular basis.
- Subjects with a high risk for severe violence or suicidality as assessed during the screening interview.
- Subjects who suffer from an unstable physical disease such as high blood pressure (>150 mmHg systolic / diastolic > 110 mmHg) or acute, unstable cardiac disease.
- History of epilepsy or seizure (EXCEPT those therapeutically induced by ECT).
- Increased risk of seizure for any reason, including prior diagnosis of increased intracranial pressure (such as after large infarctions or trauma), or history of significant head injury or trauma with loss of consciousness for ≥ 5 minutes.
- History of any metal in the head (outside the mouth).
- Metallic particles in the eye, implanted cardiac pacemaker or any intracardiac lines, implanted neurostimulators, intracranial implant (e.g., aneurysm clips, shunts, stimulators, cochlear implants, or electrodes) or implanted medical pumps.

- Individuals with a significant neurological disorder or insult including, but not limited to:
  - Any condition likely to be associated with increased intracranial pressure
  - Space occupying brain lesion
  - History of cerebrovascular accident
  - Transient ischemic attack within two years
  - Cerebral aneurysm
  - Dementia
  - Mini Mental State Exam score of less than or equal to 24
  - Parkinson's disease
  - Huntington's chorea
  - Multiple sclerosis
- Subjects suffering from frequent and severe migraine headaches.
- Subjects suffering from significant hearing loss.
- Subjects taking pro-convulsant medications (e.g., antidepressants or antipsychotic medications).
- Previous treatment with TMS.
- Subjects who cannot communicate reliably with the investigator or who are not likely to cope with the requirements of the experiment.
- Participation in a clinical trial within the last 30 days before the beginning of this clinical trial or similar participation in another clinical trial.
- Known or suspected pregnancy or lactation.
- Women of childbearing potential and not using a medically accepted form of contraception when engaging in sexual intercourse.

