Varenicline tartrate is a prescription drug marketed by Pfizer as Chantix in the U.S. (under FDA approval) and as Champix outside the U.S. Synthesized as an improvement upon cytisine, varenicline decreases the urge to smoke and reduces withdrawal symptoms. Two systematic reviews and meta-analyses supported by unrestricted funding from Pfizer, one in 2006 (Wu et al 2006) and one in 2009 (Mills et al 2009), found varenicline more effective than NRT or bupropion. A 2011 review of double-blind studies found that varenicline has increased risk of serious adverse cardiovascular events compared with placebo (Singh et al 2011). Varenicline may cause neuropsychiatric side effects; for example, in 2008 the U.K. Medicines and Healthcare products Regulatory Agency issued a warning about possible suicidal thoughts and suicidal behavior associated with varenicline (Drug Safety Update 2008).

Alternative approaches to smoking cessation include acupuncture, hypnosis, smokeless tobacco, electronic cigarettes, as well as other therapies. These methods are not legitimate smoking cessation aids as scientific studies showed no difference between these methods and placebo or no rigorous, peer-reviewed studies have been conducted.

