# **10. CONCOMITANT THERAPY**

The following medications will not be allowed throughout the study: antidepressants, stimulants, and antipsychotics indicated for psychotic episode.

The following medication will be allowed throughout the study: Insomnia medications prescribed prior to commencement of treatment may be continued during the study (up to 3mg Lorivan, or equivalent).

Only the following insomnia medications (one or more) may be prescribed during the course of the study:

- Zolipidem (p.r.n. up to 10 mg/day orally or Zolipidem CR (6.25 or 12.5 mg/day orally).
- Zaleplon ( p.r.n. up to 20 mg/day orally)
- Zopiclone ( p.r.n up to 15 mg/day orally or eszopiclone ( p.r.. up to 3 mg/day orally)
- Benzodiazepines up to a dose equivalent to 3.0 mg of Lorazepam or equivalent

Acetaminophen or other medications for treatment of local pain, dental pain or headaches will be allowed, as necessary.

Medications for general medical conditions will be allowed. All medications taken by a subject (prescription or nonprescription) must be documented in the concomitant therapy section of the CRF. This includes medications taken within 30 days before treatment initiation and during the course of the study.

For any medication given as a treatment for a new or worsening condition, the condition must be documented on the Adverse Event Form of the CRF.

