## 11.2.2. Biochemical Verification - Urine cotinine samples

Quantitative assessment of urine cotinine levels (nicotine metabolite) will be performed. Urine cotinine levels will be measured from a urine sample and sent to a core laboratory for analysis. The cotinine assessment will be performed at Baseline, at the weekly visits during the treatment phase and at the 4 month follow-up visit. The biochemical verification of cigarette smoking will be used to assess abstinence.

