11.3.1. Abstinence and Continuous Quit Rates (CQR)

Abstinence is defined as a subject's self-report (section 11.3.1) of no smoking (0

cigarettes/day), confirmed by urine cotinine levels  $\leq$ 200ng/ml (section 11.3.2). The "cutoff" value of urine cotinine) is recognized as 200 ppm or 200ng/ml) for the determination of abstinence. Subjects with cotinine levels above this value will be considered to have not stopped smoking. Continuous Quit Rates (CQR) is defined as the ratio of the number of patients meeting the quit criterion (i.e., abstinence during a consecutive 4 week period) to the number of patients initially treated, will be assessed at Baseline, at the weekly visits during the treatment phase and at the 4 month follow-up visit.

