### 13.2. Study Endpoints

# 13.2.1. Primary Efficacy Endpoint

The primary endpoint is the four-week continuous quit rate (CQR), representing abstinence during a consecutive 4 week period. Weekly abstinence is defined as a subject's self-report (in diary) of no smoking (0 cigarettes/day during the whole week), confirmed by urine cotinine levels  $\leq 200$  ng/ml. A missing confirmatory test will be considered negative, if the previous and the following weekly or 4 month follow-up confirmatory tests are negative. Quit rates are defined as the ratio of the number of patients meeting the quit criterion for at least 4 consecutive weeks to the number of patients initially treated and having at least one post-baseline assessment.

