### 13.4. Sample size

The preliminary clinical study evaluated the safety and efficacy of the DTMS as an aid in smoking cessation, at three weeks and at six months follow-up. The three week point prevalence quit rate was 44% in the treatment group and 13% in the sham group. The six month point prevalence quit rate was 33% in the treatment group and 9% in the sham group. Although, the three week point prevalence quit rate showed a significant improvement in the treatment group compared to the sham group, the point prevalence quit rate did not meet the standard requirement for evaluating smoking cessation, i.e., at least a 4 week continuous quit rate. Furthermore, the six month data had its limitations, including a long term time point and high drop-out rate. Therefore, we looked at the clinical results provided in support of FDA approval of other smoking cessation aids, including Zyban (Bupropion hydrochloride) and Chantix (Varenicline). The mechanism of action of Zyban which aids smoking cessation is the increase in dopamine release, which is also one of the mechanisms of action of the DTMS treatment.

The quit rates (i.e., based on abstinence from week 4 of the study through week 7) were 49% in the treatment group receiving Zyban compared to 36% in patients receiving Nicotine Replacement Therapy (NRT) and 23% in the placebo group. In two other studies, subjects treated with Chantix had an abstinence rate during weeks 9 through 12 of 44% compared to 30% in patients treated with Zyban and 17% and 18% in patients receiving placebo.

For the purpose of sample size calculation the weighted average of the quit rates for smoking cessation treatments (including Zyban, Chantix, NRT and DTMS) (38.6%) and the weighted average of the quit rates for placebo/sham (18.4%) will be used. Using the above weighted averages we can assume a placebo/sham success rate of 18%, and a minimally important difference of 20%.

The study is designed to have 80% power with a two-sided level of significance of 5% to detect to detect a difference of 20% in the CQR in the DTMS group compared to the control group, and one planned interim analyses using the Lan De-Mets alpha spending approach with a Pocock type spending function (the calculations were performed using the SAS SEQDESIGN procedure).

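### Section 7.3 excludes other tobacco only when it is smoked, so smokeless users are eligible and are scored as still smoking while that product keeps cotinine above 200 ng/ml

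*Protocol*

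**What the plan says.** **Entry.** Two exclusions in Protocol section 7.3 bear on other nicotine sources: "Subject is smoking any other form of tobacco or other substances" and "Currently on Nicotine Replacement Therapy (NRT) or smoking cessation drugs (e.g., Zyban, Chantix, etc.) or undergoing behavioral smoking cessation interventions". No criterion in section 7 names smokeless tobacco, e-cigarettes or nicotine products in general. The protocol does know of them. Section 2.2, after dealing with NRT and drugs, adds: "Alternative approaches to smoking cessation include acupuncture, hypnosis, smokeless tobacco, electronic cigarettes, as well as other therapies".

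**During the study.** The list of barred treatments in section 10 reads: "The following medications will not be allowed throughout the study: antidepressants, stimulants, and antipsychotics indicated for psychotic episode". No nicotine product is on it. The diary in section 11.2.1 collects cigarettes per day and time since the last cigarette.

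**Endpoint.** Section 13.2.1 has two parts: "Weekly abstinence is defined as a subject's self-report (in diary) of no smoking (0 cigarettes/day during the whole week), confirmed by urine cotinine levels" of at most 200 ng/ml. Section 11.2.2 identifies the marker: "Quantitative assessment of urine cotinine levels (nicotine metabolite) will be performed". Section 11.3.1 gives the consequence of exceeding the cut-off: "Subjects with cotinine levels above this value will be considered to have not stopped smoking".

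**Planning rates.** Section 13.4 states that "we can assume a placebo/sham success rate of 18%, and a minimally important difference of 20" percentage points.

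**The concern.** The eligibility wording and the verification rule do not fit together. The diary part of the endpoint concerns cigarettes, while the laboratory part concerns nicotine. The two agree only if cigarettes are the subject's sole nicotine source, and section 7.3 does not secure that.

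Two things are at stake. The first is misclassification: a subject who has stopped cigarettes can be counted as a failure in either arm, which lowers both quit rates and shrinks their difference. The second is interpretation: a week with a zero diary and a positive cotinine may mean concealed smoking or another nicotine product, and the procedures described do not tell these apart.

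There are smaller knock-on effects. The exploratory analysis of cigarettes per day in non-quitters would take in subjects who report none. If section 11.3.1 decides who counts as having quit, section 11.1.5 would also not require those subjects to return at 4 months.

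**Working it through.** **1. Can a smokeless user be enrolled?** Take someone who smokes at least 10 cigarettes a day, is motivated to quit, and also uses smokeless tobacco.
- Section 7.2: every inclusion criterion can be met.
- Section 7.3, other tobacco: the product is not smoked, so the criterion does not apply.
- Section 7.3, NRT and cessation aids: smokeless tobacco is neither NRT nor a cessation drug.
- Section 10: nothing bars its use after entry.

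This subject is eligible. For e-cigarettes the answer depends on whether vaping counts as smoking another substance; the text can be read either way.

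**2. How is that subject scored?** With zero cigarettes and cotinine at or below 200 ng/ml the week is abstinent. With zero cigarettes and cotinine above 200 ng/ml the subject is treated as not having stopped, whatever the source. Four consecutive abstinent weeks are needed for the primary endpoint.

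**3. Reproduce the plan's sample size.** Inputs from sections 13.4 and 13.5 with its subsections: 18% v 38%, 80% power, two-sided 5%, one interim look at about 65% information, nominal level 0.03154 at each look, 82 per arm.
- The critical value at each look is c = z(1 − 0.03154/2) = 2.15. The two test statistics have correlation √0.65. Overall two-sided alpha computes to 0.0500.
- Unpooled variance: v = 0.18×0.82 + 0.38×0.62 = 0.3832.
- Drift needed for 80% power: 2.914. Then n = 2.914² × 0.3832 / 0.20² = 81.4, so 82 per arm, as stated.
- Power at 82 per arm: drift 0.20/√(0.3832/82) = 2.93, which gives 80.3%.

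**4. Add the dilution.** Let f be the share of each arm that always fails because of another nicotine source. The documents give no value; 0 to 20% is an assumption. Both rates are multiplied by (1 − f), v is recomputed, and drift is difference/√(v/82).

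| f | Sham | DTMS | Difference | v | Drift | Power at 82 per arm | n per arm for 80% |
|---|---|---|---|---|---|---|---|
| 0% | 18.0% | 38.0% | 20.0 | 0.3832 | 2.93 | 80.3% | 82 |
| 2% | 17.6% | 37.2% | 19.6 | 0.3790 | 2.88 | 79.1% | 84 |
| 5% | 17.1% | 36.1% | 19.0 | 0.3724 | 2.82 | 77.3% | 88 |
| 10% | 16.2% | 34.2% | 18.0 | 0.3608 | 2.71 | 74.1% | 95 |
| 20% | 14.4% | 30.4% | 16.0 | 0.3348 | 2.50 | 67.0% | 112 |

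**5. Sensitivity to the test level.** The heading of section 13.5 says that the interim analysis was not performed. A single look at two-sided 0.05, simulated for a pooled two-proportion test with 82 per arm, gives power of 82, 80, 77 and 70% for f = 0, 5, 10 and 20%. The loss is of similar size.

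**The case against.** Several stronger readings are tempting, and the documents do not support them.

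- **That users of other nicotine products cannot meet the endpoint.** Failure requires cotinine above 200 ng/ml, not merely some nicotine. The protocol gives no cotinine levels for smokeless or e-cigarette use. Light or intermittent users, and those who stop all nicotine, may pass.
- **That e-cigarettes are plainly allowed.** The criterion also mentions other substances, and the protocol uses the word smoking loosely elsewhere; section 6 asks participants to refrain from smoking nicotine. A site could fairly take vaping as excluded. What stands is the ambiguity, which sites may resolve differently.
- **That the trial is biased.** Allocation is 1:1 and stratified by site, so there is no reason to expect more such subjects in one arm. Counting a nicotine-positive subject as a failure does not favour the device.
- **That the power loss is established.** The share f covers only those who keep using the product, stay above the cut-off, and would otherwise have quit at the average rate. At 2% the loss is about one point. The model also treats 18% and 38% as free of such users, although section 13.4 derives them from earlier studies whose populations may have included some.

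Two further objections carry weight. Screening already records smoking history and habits (section 11.1.2), so some dual users may be identified there, although no criterion would then exclude those using a smokeless product. The past tense in section 13.4 on dropout monitoring, and the note on the interim analysis in section 13.5, suggest that this version was written late in the trial, when a new entry criterion could change little.

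None of this removes the mismatch between the exclusion wording and the cotinine rule for smokeless tobacco.

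**Conclusion.** The point holds in a limited form. Section 7.3 leaves smokeless tobacco users eligible and is unclear on e-cigarettes, while sections 11.3.1 and 13.2.1 score a subject by a nicotine metabolite whatever its source. A subject who stops cigarettes can be counted as a failure for as long as the other product keeps cotinine above the cut-off.

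The consequence is attenuation in both arms and some loss of power, with no expected inflation of type I error. The size cannot be established from the protocol. The power figures rest on an assumed f, on equal shares in the two arms, and on planning rates free of such users. Because the design starts at 80.3%, even an assumed 2% takes it just below target, but the true share may be negligible. The change is worth making because it is cheap, not because the loss is shown to be large.

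**What to change.** - Reword the section 7.3 criterion to exclude current use of any tobacco- or nicotine-containing product other than cigarettes, smoked or not, naming smokeless tobacco and e-cigarettes.
- Ask subjects not to start such a product through week 6, and record any use at the weekly visits already scheduled.
- Leave the primary cotinine rule as it is, so that the endpoint is not loosened.

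The cost is one reworded line and one extra question at existing visits; a few dual users are lost at screening.

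If enrolment is already closed, the new wording cannot change who was enrolled. In that case add a sensitivity display, by arm, of weeks with 0 cigarettes in the diary and cotinine above 200 ng/ml. It uses data already collected. It can separate other nicotine use from concealed smoking only where such use was recorded.
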